#### 9.5 Rescue treatment

In case subjects require additional treatment for atopic dermatitis during the treatment phase, as a first step, TCS / TCIs are recommended, and administration of study drug will be continued. Should other systemic AD therapy be required (e.g., cyclosporin A, oral JAK inhibitors, oral corticosteroids), the IMP administration should be stopped, and the subject will be withdrawn from the trial. Any use of AD therapy other than the trial treatment (see also section 9.7) needs to be documented in detail in the eCRF including use of emollients (see also section 9.4.)

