## 9.7 Prohibited medication(s) and procedures

The medications and/or procedures listed in Panel 5 are prohibited during the trial. Details regarding prohibited medications and/or procedures prior to screening and during wash-out(s) are described in Section 8.3.

Panel 5: Prohibited medication(s) and/or procedure(s)

Medication or procedure	Prohibited from	Prohibited to
TCS, TCI or topical PDE-4 inhibitors.	7 days prior to baseline (Washout).	Week 16.
Other topical prescription medications or prescription emollients/moisturisers (other than the ones allowed during treatment period) used for the treatment of AD.	7 days prior to baseline (Washout).	Week 16.
Intake of nonsteroidal anti- inflammatory drugs (NSAIDs), except Paracetamol	7 days prior to baseline	Week 16.
Use of UVA, UVB, PUVA, other phototherapy, or tanning beds.	4 weeks prior to baseline.	Week 16.
Immunoglobulin or blood products.	4 weeks or 5 half-lives prior to baseline, whichever is longer.	Safety follow-up (week 32).
Systemic corticosteroids (excluding inhaled or intranasal steroids).	4 weeks prior to baseline.	Safety follow-up (week 32). If medically indicated and deemed necessary at investigator's discretion a patient may receive therapies with systemic corticosteroids during the safety follow-up.
Systemic immunosuppressive/immuno-modulating medication, (excluding systemic antihistamines if taken at a stable dose before baseline), e.g., JAK inhibitors.	2 weeks or 5 half-lives prior to baseline, whichever is longer.	Safety follow-up (week 32). If medically indicated and deemed necessary at investigator's discretion a patient may receive therapies with systemic corticosteroids during the safety follow-up.

Medication or procedure	Prohibited from	Prohibited to
Biologics	16 weeks or 5 half-lives prior to baseline, whichever is longer.	Safety follow-up (week 32). If medically indicated and deemed necessary at investigator's discretion a patient may receive therapies with systemic corticosteroids during the safety follow-up.
Allergen immunotherapy.	4 weeks prior to baseline.	Safety follow-up (week 32). If medically indicated and deemed necessary at investigator's discretion a patient may receive therapies with systemic corticosteroids during the safety follow-up.
Live (attenuated) vaccine.	12 weeks prior to baseline.	Safety follow-up (week 32).

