### 10 Discontinuation and withdrawal

## 10.1 General principles

A subject may withdraw from the trial (prior to first dose or during the treatment period) or permanently discontinue trial treatment at any time if the subject, the investigator, or LEO Pharma considers that it is not in the subject's best interest to continue.

A subject who withdraws from the trial is a subject who stops treatment with the IMP and all further protocol defined trial activities. A subject who permanently discontinues IMP is a subject who, although they stop treatment with the IMP, agree to their follow-up as described in Section 10.3. Early termination assessments to be conducted for both events are described in Section 10.3.

If a subject withdraws from the trial, they may request destruction of any samples taken and not tested. The investigator must document this in the subject's medical record and inform LEO Pharma.

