#### 10.2 Reasons for discontinuation of IMP

### 10.2.1 Reasons for permanent discontinuation of IMP

Subjects will permanently discontinue IMP in the event of:

- Withdrawal by subject
- An AE that, in the opinion of the investigator or sponsor's medical expert, contraindicates further dosing.
- Confirmed clinically significantly abnormal ECG or change in ECG.
- Initiation of prohibited medication which cannot be safely replaced by other non-prohibited medications.
- Evidence of pregnancy, or if the subject is noncompliant with the contraception requirements (see Section 8.2).
- Symptomatic infection with SARS-CoV-2 that is likely to have an impact on efficacy or safety data (i.e., patients with a SARS-CoV-2 infection without or very mild symptoms only (e.g., rhinitis or sore throat) might continue with the study at investigator's discretion and in accordance with the applicable local regulations)..
- Other reasons, at the discretion of the investigator. If other, a specification should be provided.

Page 66 of 129

It is not allowed to restart IMP treatment after discontinuation of IMP.

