## 14.3.7 Analysis of exploratory efficacy endpoints

## **Binary endpoints**

The endpoints

- Having a decrease in EASI of at least 50% (EASI 50) from baseline to week 1, 2, 4, 6, 8, 12, and 16, assessed separately.
- Having a decrease in EASI of at least 75% (EASI 75) from baseline to week 1, 2, 4, 6, 8, 12, and 16, assessed separately.
- Having a decrease in EASI of at least 90% (EASI 90) from baseline to week 1, 2, 4, 6, 8, 12, and 16, assessed separately.
- Having vIGA-AD score of 0 (clear) or 1 (almost clear) at week 1, 2, 4, 6, 8, 12, and 16, assessed separately.

will be analysed on the full analysis set by computing frequency tables for each time point by treatment group.

Proportions with respect to these endpoints will be plotted by treatment group.

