## 14.3.12 General principles

All data will be analysed descriptively. No formal significance tests will be performed. Efficacy analyses will be based on the FAS, and safety analyses will be based on the safety analysis set. PK summary will be based on the PK analysis set.

If not mentioned otherwise, endpoints will be summarised descriptively at each visit by treatment. For endpoints evaluated over time, plots will be made to explore the trajectories with time.

An observed cases approach will be used for tabulations of data by visit (that is, involving only those subjects who attended each specific visit). The number of subjects for whom data was not collected at each specific visit will also be provided.

Categorical data will be summarised by treatment group, using the number and percentage of subjects in each category. Continuous data will be summarised using the mean, median, standard deviation (SD), 1st quartile, 3rd quartile, minimum, and maximum values. Additionally, geometric mean and coefficient of variation (CV) will be provided for the PK endpoint.

In general, for endpoints evaluated as change from baseline and/or where a baseline adjustment is applied, baseline is defined as assessments conducted at the randomisation visit (visit 3), if not otherwise stated. If the information is not available at the randomisation visit but at the (re)screening visit (visit 1) then this will be used instead.

All the analyses specified in the protocol will be reviewed in relation to the blinded data actually obtained, and the statistical analysis plan will be finalised before breaking the randomisation code.

Any changes from the statistical analyses planned in this clinical trial protocol will be described and justified in a protocol amendment, the statistical analysis plan, and/or in the CTR, dependent on the type of change.

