1	Treatment with systemic immunosuppressive/immunomodulating medication (excluding systemic antihistamines if taken at stable dose already before baseline) e.g JAK inhibitors, immunoglobulin/blood products within 2 weeks or 5 half-lives prior to baseline, whichever is longer.	To not interfere with primary endpoint and efficacy assessments.	
2	Treatment with systemic corticosteroids within 4 weeks prior to baseline	To not interfere with primary endpoint and efficacy assessments	
3	Intake of nonsteroidal anti-inflammatory drugs (NSAIDs) within 1 week prior to baseline. Intake of paracetamol will be allowed.	To not interfere with primary endpoint and efficacy assessments	
4	Treatment with biologics within 5 half-lives (if known) or 16 weeks prior to baseline, whichever is longer.	To not interfere with primary endpoint and efficacy assessments	
5	Allergen immunotherapy within 4 weeks prior to baseline	To not interfere with primary endpoint and efficacy assessments	
6	Treatment with TCS, TCI, topical PDE-4 inhibitor, or other topical prescription treatments within 1 week prior to baseline.	To not interfere with primary endpoint and efficacy assessments	
7	Use of tanning beds or phototherapy (narrow band ultraviolet B [NBUVB], ultraviolet B [UVB], ultraviolet A1 [UVA1], psoralen + ultraviolet A [PUVA]) within 4 weeks prior to baseline	To not interfere with efficacy assessments	

Trial ID: LP0145-2274

THIS DOCUMENT CONTAINS CONFIDENTIAL INFORMATION AND MUST NOT BE COPIED OR MADE AVAILABLE TO ANY THIRD PARTY WITHOUT THE PRIOR WRITTEN CONSENT OF THE LEO PHARMA GROUP

Date: **04-Jan-2023** Version: 5.0

8	Treatment with a live (attenuated) vaccine within 12 weeks prior to baseline.	To ensure safety of subjects as LEO 138559 could potentially interact with this.
9	Active dermatologic condition that could confound the diagnosis of AD or interfere with assessment of the treatment.	To exclude conditions that are likely to interfere with the assessment of severity of AD.
10	History of malignancy within 5 years prior to randomization, apart from nonmetastatic BCC, SCC of the skin, or cervical carcinoma in-situ, considered cured by the standard of care.	To ensure safety of subjects.
11	Clinically significant active chronic or acute infection requiring systemic treatment within 4 weeks prior to baseline that may compromise the safety of the subject	To ensure safety of subjects
12	Skin infection within 1 week prior to the baseline visit.	To ensure safety of subjects

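### Section 9.5 recommends topical rescue that Panel 5 prohibits to week 16, and the observed-case responder tables can count a rescued attendee as a responder without flagging it

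*Combined protocol and SAP*

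**What the plan says.** **Rescue.** For subjects who need more treatment for atopic dermatitis (AD) during the treatment phase, protocol section 9.5 says: "as a first step, TCS / TCIs are recommended, and administration of study drug will be continued". If systemic AD therapy is needed, "the IMP administration should be stopped, and the subject will be withdrawn from the trial". All such treatment has to be entered in the eCRF.

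**Prohibition.** Panel 5 in section 9.7 lists "TCS, TCI or topical PDE-4 inhibitors" as prohibited from seven days before baseline up to week 16. That row has no rescue exception. Among the grounds for permanently stopping study drug (IMP), section 10.2.1 lists "Initiation of prohibited medication which cannot be safely replaced by other non-prohibited medications", and IMP may not be restarted afterwards. The closing paragraph of section 9.7 requires any prohibited treatment to be recorded and the sponsor's medical expert to be told at once.

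**Analysis.** Under section 14.3.7 the EASI 50/75/90 and vIGA-AD 0/1 endpoints "will be analysed on the full analysis set by computing frequency tables for each time point by treatment group". Section 14.3.12 adds: "An observed cases approach will be used for tabulations of data by visit (that is, involving only those subjects who attended each specific visit". It also promises the number of subjects without data at each visit. Section 14.3.13 leaves missing values to the SAP. Nothing in sections 14.2 to 14.3.13 says how data collected after rescue are treated. For the primary endpoint, section 14.1 calls a subject evaluable once lesional biopsies exist at baseline and week 4, and section 14.3.5 summarises the change by arm.

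**The concern.** There are two linked problems.

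The first is conduct. An investigator facing a flare in the first weeks can follow section 9.5 (give TCS/TCI, continue IMP) or section 9.7 (avoid TCS/TCI, and if they cannot be avoided consider a permanent stop). The choice falls before the week-4 biopsy, which carries the primary endpoint. The protocol itself treats these drugs as able to disturb that endpoint: Appendix 5 justifies their washout before baseline with "To not interfere with primary endpoint and efficacy assessments".

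The second is analysis. A rescued subject who keeps attending has observed data, so the attendee-only rule keeps that subject in the responder tables. If the skin clears with the help of TCS/TCI, the tables show a response on the assigned antibody. Section 12.1 uses the comparator as the reference for efficacy as well as mechanism, so in arms of 8 and 4 one such subject can visibly change the comparison a reader draws.

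**Working it through.** **Step 1: can the two rules be read together?** Section 9.5 refers to section 9.7 only when it asks for documentation, not as an exception to it. Section 7.1 permits topical AD treatment in the safety follow-up, which suggests it is not permitted earlier. The notification duty in section 9.7 tells the sponsor that a prohibited drug was used. It does not say whether rescue under section 9.5 is prohibited use. The text leaves the matter open.

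**Step 2: effect of a rescued attendee on a responder rate.** The plan states no figure to reproduce, because the sample size is not power-based. The only stated numbers are the arm sizes in section 14.1: 12 × 2/3 = 8 and 12 × 1/3 = 4. Let a be unrescued responders, b rescued responders, w subjects absent from the visit, and n the arm size.

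- Observed-case rate: (a + b)/(n − w)
- Rate counting rescue and exit as non-response: a/n

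With b = 1 and w = 0 the gap is 1/n, whatever a is. The counts below are assumed, with a = n/2:

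| Arm | Observed case | Rescue as non-response | Gap |
|---|---|---|---|
| n = 8, a = 4 | 5/8 = 62.5% | 4/8 = 50.0% | 12.5 points |
| n = 4, a = 2 | 3/4 = 75.0% | 2/4 = 50.0% | 25.0 points |

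A rescued attendee who still does not respond creates no gap.

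**Step 3: absent subjects, a separate mechanism.** Now b = 0 and w = 1, against a reference rate of 50%:

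- One withdrawn non-responder: 4/7 = 57.1% (+7.1 points) or 2/3 = 66.7% (+16.7).
- One responder who leaves for an unrelated reason, n = 8: observed 3/7 = 42.9% (−7.1); exit as non-response 3/8 = 37.5% (−12.5).
- The same, n = 4: observed 1/3 = 33.3% (−16.7); exit as non-response 1/4 = 25.0% (−25).

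Algebraically (a + b)/(n − w) ≥ a/n, so the observed-case rate is never the lower of the two. The unrelated-exit cases show that neither rate has a fixed direction of error against the true rate.

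**Step 4: would the planned output reveal a rescued attendee?** Disposition by last visit (14.3.1), missing counts (14.3.12) and individual plots (14.3.5, 14.3.7) reveal subjects who leave. Concomitant medication appears only among baseline characteristics (14.3.2). Important protocol deviations are described in the trial report (Appendix 3D), but the conflict in Step 1 leaves it unclear whether rescue is a deviation. No planned table marks the subject.

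**Step 5: the week-4 biopsy.** If rescue shifts one subject's biomarker change by s, the arm mean moves by s/8 = 0.125s or s/4 = 0.25s. The documents give no value for s. It may be zero, because section 11.6.3 lets a biopsy between baseline and end of treatment come from another representative lesion.

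**The case against.** The strongest reply is that section 9.5 is the specific rule and says plainly that study drug continues. Section 10.2.1 applies only when the prohibited drug cannot be safely replaced. There is one site and about 12 subjects, and every use of TCS/TCI is recorded and escalated. This narrows the practical room for confusion, but it does not settle which rule governs or whether rescue is a deviation.

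A reader might infer more than the text supports, in four ways:

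- *That withdrawn subjects leave the denominator because a rescue rule is lacking.* They do not. Section 10.1 states: "A subject who withdraws from the trial is a subject who stops treatment with the IMP and all further protocol defined trial activities". Such a subject has no later data for a rescue rule to govern. This is a missing-data matter, sent to the SAP by section 14.3.13, and the missing counts make it visible.
- *That the SAP has no rule.* No separate SAP text is supplied. Section 14.3.12 has it finalised after review of blinded data and before the code is broken, so a rule can still be set. The deferral in section 14.3.13 names missing values, though, and post-rescue data are observed, so it does not clearly cover them.
- *That the observed-case rates are inflated.* Step 3 shows the direction against the true rate is not fixed.
- *That week-4 biopsies after stopping IMP enter the primary summary by oversight.* Footnote b to Panel 2 and section 10.3 deliberately bring these subjects back for a nominal week-4 visit. Keeping them is a legitimate choice, and section 11.6.3 promises a detailed separate biopsy report.

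**Conclusion.** The point holds in limited form. The conflict between section 9.5 and Panel 5 stands in the current text, and section 10.2.1 attaches a possible irreversible consequence to it. The observed-case rule lets a topical-rescued attendee count as a responder, and no planned table shows it. The size is 12.5 points per rescued responder at n = 8 and 25 points at n = 4, measured against counting rescue as non-response. This assumes that at least one such subject occurs; the documents give no rescue, withdrawal or response rates. The responder endpoints are exploratory and no formal tests are planned. For the primary endpoint, interference from a topical is possible but not shown. Severity is minor to moderate: the conduct wording should be corrected, and the analysis part is a reporting safeguard.

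**What to change.** - **(a) Protocol.** Add to Panel 5 and section 10.2.1 an exception for TCS/TCI rescue given under section 9.5.
- **(b) SAP, before unblinding.** Specify a supplementary responder table with the full analysis set as denominator, beside the observed-case table. Count a subject as a non-responder after TCS/TCI or systemic AD rescue, withdrawal or IMP discontinuation. State a rule for visits missed for other reasons, for example non-response at that visit only. Flag rescued subjects and non-efficacy exits; section 10.2.1 already codes the reasons.
- **(c) Primary endpoint.** Keep all week-4 biopsies in the summary. Flag those taken after TCS/TCI use or IMP stop in the individual plots or a listing, and optionally show the summary without them as a sensitivity display. Base the flag on medication and dosing dates. Matching by site is not feasible: section 9.6 records the location of topicals with laterality, but section 11.6.3 records biopsies only as upper limb, lower limb or trunk.

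**Cost.** Item (a) is one clause but may be a substantial amendment needing authority and ethics approval (Appendix 3A). Items (b) and (c) need SAP wording, one extra table and a listing or plot flag, from data already collected. Table (b) will show lower response rates if such cases occur and will score unrelated exits as failures, which is why the observed-case table stays beside it.

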## 14.3.13 Handling of missing values

Handling of missing values will be specified in the statistical analysis plan (SAP).

Page 101 of 129

For the weekly average of worst daily pruritus NRS, a minimum of four measurements per week must be available, otherwise the score for this week will be set to missing.

# Appendix 1: Definitions of adverse events and serious adverse events

#### Adverse event definition

An AE is defined as any untoward medical occurrence in a patient or clinical investigation subject administered a pharmaceutical product and which does not necessarily have a causal relationship with this treatment. An AE can therefore be any unfavourable and unintended sign (including an abnormal laboratory finding), symptom, or disease temporally associated with the use of a medicinal (investigational) product, whether or not related to the medicinal (investigational) product [57].

#### This definition includes:

- Accidental injuries.
- Events related to trial procedures.
- Reasons for any unfavourable and unplanned change in medication (drug and/or dose).
- Clinically significant worsening of pre-existing conditions.
- Reasons for admission to hospital or surgical procedures\*.
- AEs commonly observed and AEs anticipated based on the pharmacological effect of the IMP.
- Any laboratory abnormality assessed as clinically significant by the investigator (see Section 11.4.5.2).

#### Serious adverse event definition

An SAE is any untoward medical occurrence that:

- Results in death.
- Is life-threatening at risk of death at the time of the SAE (not an event that hypothetically might have caused death if more severe).
- Requires inpatient hospitalisation or prolongation of existing hospitalisation\*.
- Results in persistent or significant disability or incapacity.
- Is a congenital anomaly or birth defect.
- Is a medically important condition. Events that may not be immediately life-threatening or result in death or hospitalisation but may jeopardise the subject or may require intervention to prevent one of the other outcomes listed in the definition above. Examples are intensive treatment in an emergency room or at home for allergic bronchospasm, blood dyscrasias, and convulsions that do not result in hospitalisation, development of drug dependency, or drug abuse.

Page 107 of 129

- \*Hospitalisation for procedures or treatments planned prior to the subject consented to trial participation does not constitute an AE and should therefore not be reported as an AE or SAE.
- \*Hospitalisation for elective treatment of a pre-existing condition which did not worsen from the subject consented to trial participation is not considered an AE and should therefore not be reported as an AE or SAE, even if not planned before consent to trial participation.
- \*Hospitalisation for routine scheduled treatment or monitoring of the studied indication not associated with any aggravation of the condition does not constitute an AE and should therefore not be reported as an AE or SAE.
- \*Hospitalisation for administrative, trial-related, or social purpose does not constitute an AE and should therefore not be reported as an AE or SAE.
- \*Complications that occur during hospitalisation are (S)AEs. If a complication prolongs hospitalisation, the event is an SAE.
- \*When in doubt as to whether hospitalisation occurred or was necessary, the AE should be considered serious.

Trial ID: LP0145-2274 Date: **04-Jan-2023** Version: 5.0

Page 108 of 129

### Appendix 2: Classification of adverse events

### Severity

The *severity* of the AE should be described in terms of mild, moderate, or severe according to the investigator's clinical judgement. If the AE worsens in severity, the new severity, including date of worsening, should be recorded. However, if an AE with onset prior to IMP initiation worsens after IMP administration, a new AE should be recorded.

Mild	An AE that is usually transient and may require only minimal treatment or therapeutic intervention. The event does not generally interfere with usual activities of daily living.
Moderate	An AE that is usually alleviated with additional specific therapeutic intervention. The event interferes with usual activities of daily living, causing discomfort, but poses no significant or permanent risk of harm to the subject.
Severe	An AE that interrupts usual activities of daily living, or significantly affects clinical status, or may require intensive therapeutic intervention.

